### Statistical analysis:

The planned analyses include a linear mixed model-approach to account for the effect of unit, degree of prematurity and intervention. Variables that will be considered for inclusion into the model are gestational age at birth, mode of delivery, birth weight z-score, plurality, neonatal morbidities, and receipt of antenatal steroids.

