## Background

In Europe, over 500,000 newborn infants are hospitalized each year. Infants are often separated from their parents during their hospitalization. One study showed that very preterm infants spent 80% of their time without any human contact (1). A European survey showed a large variation in parents' presence between hospitals, starting from 2.6 hours per day (unpublished data). Even when present, the parents are often just bystanders.(2,3) Separating the child from the parents places the socio-emotional and cognitive development at risk.(4,5) Studies have shown that parental involvement during hospitalization facilitates growth, socio-emotional, cognitive and linguistic development in preterm infants.(6-9)

An intervention directed at empowering parents shortened the length of stay by 3.9 days in preterm infants.(10) Vohr et al. showed that in settings with single-family room architecture, the infants of actively participating mothers had on average 15 days shorter length of stay compared to infants of non-active mothers. Interventions aimed at family-centered care are heterogeneous and their effects vary. In a meta-analysis comprising seven studies on family-centered care interventions, the length of stay was unaffected, but on the other hand e.g. preterm subpopulations were not considered.(11)

Parental presence can also be encouraged by hospital architecture. Even if modern hospitals nowadays include facilities also for parents based on the beneficial effects of single-family rooms (12,13), only 13.3% of 331 neonatal units provided parents with the facilities needed to stay with their infant throughout a 24-hour day.(14) Single-family rooms shortened the length of stay by 10 days among very preterm infants born before 30 gestational weeks in a randomized setting in Stockholm.(15) Also single-family room models are heterogeneous; according to a loose definition three solid walls suffices to qualify as single-family room, and does not necessarily include beds for the parents. A meta-analysis of 12 different single-family room studies did not show any significant benefit regarding length of stay compared to traditional hospital architecture.(16) However, in this meta-analysis most studies were observational studies without control groups; only one randomized study was included and no causal inferences could be drawn.

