The Close Collaboration with Parents training program has been developed in Turku University Hospital, Finland. It is a structured and comprehensive training program for neonatal staff aiming to support parenthood and parental involvement in neonatal intensive care. The program addresses staff attitudes by reflection and exercises. The program has been shown to improve implementation of family-centered care in the varying contexts of neonatal intensive care units in both regional hospitals and university hospitals. After the completion of the training program, parents spent more time with their child during hospitalization.(17) Nurses reported that the training program strengthened the family-centered care culture and that the program enforced the role of the parents as primary caregivers.(18,19) Breast feeding was commenced on average three weeks earlier than before the training program, skin-to-skin care was commenced earlier and the amount of skin-to-skin care increased. The weight gain of premature infants improved by 44.5%, and the mothers of very preterm infants suffered from fewer depressive symptoms.(20,21)

It is imperative to study the economic impact of extensive, resource-demanding interventions that affect a whole neonatal unit. The Close Collaboration with Parents training program has so far been implemented in 11 neonatal units in Finland. In addition, four units have changed to single-family room architecture between 2014 and 2019. The national health care registers kept by the Institute for Health and Welfare contain a fully population-based dataset comprising all newborn infants (Medical Birth Register), hospitalizations and outpatient visits (Hospital

Discharge Register). These data are available since 1987, and enable retrospective research on the health and care of newborn infants. In Finland, we currently have a unique opportunity to study the effects of both a family-centered care intervention and single-family room architecture in more controlled circumstances than in previous studies: the interventions have been performed systematically throughout the country; societal support such as paid parental leave and universal access to health care grant all parents the same opportunities to participate; the register data are comparable for all units; and preterm infants can be studied as a separate group.

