### **Description of the interventions: Two interventions are studied (Figure 1)**

- Close Collaboration with Parents-training program in 11 neonatal units
- Adoption of single-family room architecture in 4 neonatal units
- Control group: Infants cared for in the 10 neonatal units where neither of the interventions have been implemented.

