### Outcomes:

The *primary* outcome is the length of stay during the initial hospitalization to neonatal care. Comparisons will be made between infants cared for in intervention units and those cared for in non-intervention units.

*Secondary* outcomes are:

Corrected gestational age at discharge

The amount of outpatient visits after discharge during the first year of life

Growth parameters (weight, length, head circumference) at discharge compared to national standards

Change in growth parameters from birth to discharge

Cost effectiveness (according to hospitalization cost analyses carried out by the Institute for Health and Welfare)

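### The primary comparison has no dated exposure rule and no calendar-time term, although births span 2006–2020 and the room units changed over only in 2014–2019

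*Combined protocol and SAP*

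**What the plan says.** The Outcomes section defines the primary comparison by unit alone: "Comparisons will be made between infants cared for in intervention units and those cared for in non-intervention units". The section describing the interventions defines the control group as "Infants cared for in the 10 neonatal units where neither of the interventions have been implemented". It gives no status to infants born in an adopting unit before adoption.

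The Statistical analysis section says: "The planned analyses include a linear mixed model-approach to account for the effect of unit, degree of prematurity and intervention". The candidate list begins "Variables that will be considered for inclusion into the model are gestational age at birth, mode of delivery" and continues with birth weight z-score, plurality, neonatal morbidities and antenatal steroids. Birth year, period and a before/after term do not appear.

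Methods sets the birth window at 1 January 2006 to 31 December 2020. Background says that "four units have changed to single-family room architecture between 2014 and 2019". For the training program it gives a count of 11 units and no dates. The intervention heading points to a figure ("Two interventions are studied (Figure 1"), which is not reproduced in the text available here and may show dates.

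**The concern.** Every room unit contributes 8 to 14 of its 15 birth years from before its rooms existed. How those births are handled decides what the primary result means, and three contrasts fit the text:

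- **(a) Fixed unit label.** All births in an adopting unit count as exposed, including those before adoption.
- **(b) Dated exposure, unit effect, no time term.** The estimate is essentially before versus after within adopting units.
- **(c) Post-switch births against control births of all years.** Later births are compared with births that are earlier on average.

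Under (a) a real effect is diluted, whether or not length of stay was changing over time. Under (b) and (c) any trend that the covariates do not explain is read as an intervention effect. A unit effect does not remove a trend shared by all units.

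This also undercuts the stated rationale. Background faults the earlier room literature because "most studies were observational studies without control groups" and presents this study as done "in more controlled circumstances than in previous studies". Under (b) without a time term, the control units do almost nothing to separate trend from effect.

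**Working it through.** The plan states no effect size, SD or sample size for this comparison, so there is no figure of its own to reproduce. The first part uses only the stated dates and an assumption of even births.

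**From the documents' dates.** Let the window run from 0 (start of 2006) to 15 (end of 2020), with a unit switching at time s. For the room units s lies between 8 (start of 2014) and 14 (end of 2019).

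- **(a)** Exposed share = (15 − s)/15, which is 7/15 = 46.7% at s = 8 and 1/15 = 6.7% at s = 14. Background cites a 10-day effect of single-family rooms in infants born before 30 weeks. An effect of that size would show as 10 × 7/15 = 4.7 days down to 10 × 1/15 = 0.7 days. These are single-unit extremes. With assumed switches at the start of 2014, 2016, 2017 and 2019, the average share is (7 + 5 + 4 + 2)/60 = 30%.
- **(b)** Mean post-switch time minus mean pre-switch time = (s + 15)/2 − s/2 = 7.5 years for every s. A residual trend of 0.1 day per year (assumed) would appear as a 0.75-day effect.
- **(c)** Mean post-switch time minus mean control time = (s + 15)/2 − 7.5 = s/2, which is 4.0 to 7.0 years of trend.

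The range in (a) is for rooms only, because the text gives no training dates.

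**Illustration of the trade-off under (b); all inputs beyond the unit counts are assumed.** Generalised least squares on unit-year means with a random unit intercept and known variances; 4 room, 11 training and 10 control units without overlap; room starts 2014, 2016, 2017 and 2019; training starts spread over 2009–2014, 2012–2018 or 2014–2019; within-unit SD 15 days, unit SD 3 days; no covariates; one linear trend common to all units.

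- Bias per 1 day/year of trend: 7.2–7.5 days without year terms, 0 with them.

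| SE at 100 infants per unit-year (days) | Without year terms | With year terms |
|---|---|---|
| Rooms | 0.436 | 0.472–0.480 |
| Training | 0.245–0.261 | 0.308–0.329 |

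Year terms lower the mean squared error once the residual trend exceeds √(SE_with² − SE_without²) / bias multiplier. For rooms with the earliest training starts: √(0.472² − 0.436²)/7.5 = 0.181/7.5 = 0.024 day/year.

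| Infants per unit-year | Break-even trend (day/year) |
|---|---|
| 30 | 0.044–0.049 |
| 100 | 0.024–0.027 |
| 300 | 0.014–0.016 |

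At 100 infants this is about 0.4 day in total over 15 years (0.024 × 15 = 0.36; 0.027 × 15 = 0.41). Adding an assumed unit-by-year SD of 1.5 days raises the 100-infant threshold to 0.034–0.038. Below the threshold the model without year terms does better.

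**The case against.** Several points on the other side have weight.

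- **Figure 1 may hold the adoption dates.** This stands as a limit on the exposure half of the point. Dates alone would still not say how pre-adoption and transitional infants are classified, and they would not put time in the model.
- **The text is brief rather than exclusive.** The analyses are said to include a mixed model, and the covariates are ones to be considered, so a time term is not ruled out. That is correct, but none is planned, and leaving it open lets the contrast be chosen after the data are seen.
- **Reading (a) is not the most natural one.** Elsewhere the text speaks of adoption and of interventions having been implemented, which fits dated exposure better. With fixed unit effects, a never-changing label could not be estimated at all, so (a) needs random unit effects. Both remarks are fair. Yet the sentence that defines the primary comparison is by unit only, and no passage states a date rule.
- **Harm under (b) and (c) is conditional.** No trend is reported, the covariates may absorb part of one, and with none (b) carries no trend bias and is more precise. This stands.
- **The day figures do not describe this cohort.** The 10-day effect comes from infants born before 30 weeks, while the cohort is all newborns needing neonatal care. The dilution percentages carry over; the days are only a scale.
- **The break-even values rest on assumed inputs.** This also stands: they move with unit size and variance, as shown above. The case for the change does not depend on them.

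**Conclusion.** The concern holds. As written, the plan does not identify the primary contrast, and this should be settled before analysis. Two results follow from the stated dates and even births alone: a fixed unit label would leave 47% down to 7% of a room effect in any one unit, and dated exposure without a time term would multiply any residual trend by about 7.5. The first needs no trend; the second matters only if a trend remains after covariate adjustment. The finding concerns the readable text, since Figure 1 could not be seen. Confidence is highest for the absent time term, which a figure of dates would not supply.

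**What to change.** In the Outcomes and Statistical analysis sections:

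1. Define each infant's exposure by unit and admission date relative to that unit's adoption of each intervention, citing Figure 1 if it holds the dates.
2. Keep pre-adoption births in adopting units as unexposed, alongside births in the 10 control units.
3. Add categorical birth-year effects and a separate time-varying indicator for each intervention to the mixed model with unit effects.
4. State in advance how infants admitted during the training period, and stays that span a switch, are classified.

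Useful supporting analyses are a display of pre-adoption trends in adopting and control units, a unit-by-year random effect, and an analysis by time since adoption, because a change in staff practice may build up gradually.

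**Cost.** No new outcome data are needed. The team must assemble adoption dates and fix two classification rules. The reference list includes a before-and-after study of the training in nine units, which suggests, but does not prove, that dates exist for many of them. Under the assumed values at 100 infants per unit-year, year terms raise the standard error by about 25% for training and 8–10% for rooms. The revised model still relies on a trend common to adopting and control units, and the plan should say so.

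### No parental characteristic fixed before birth is among the candidate covariates, so differences in parent mix between non-randomised units or over time could bias the length-of-stay effect in either direction

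*Combined protocol and SAP*

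**What the plan says.** The Statistical analysis section plans a "linear mixed model-approach to account for the effect of unit, degree of prematurity and intervention". It continues: "Variables that will be considered for inclusion into the model are gestational age at birth, mode of delivery, birth weight z-score, plurality, neonatal morbidities"; antenatal steroids complete the list. It does not say whether unit is a fixed or a random effect, or whether an infant's exposure depends on the date of birth relative to the unit's adoption date.

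For the primary outcome, the Outcomes section says "Comparisons will be made between infants cared for in intervention units and those cared for in non-intervention units". The interventions section lists 11 training-program units, 4 single-family-room units and 10 units with neither. Nothing is randomised.

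The Background gives the rationale. It reports that parents spent more time with their child after the training, and that in single-family-room settings "the infants of actively participating mothers had on average 15 days shorter length of stay compared to infants of non-active mothers". On the comparability of parents it says only that "societal support such as paid parental leave and universal access to health care grant all parents the same opportunities to participate".

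The Methods section requests background data from the Hospital Discharge Register and the Medical Birth Register, without naming any parental item.

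**The concern.** If parental involvement shortens stay, as the plan supposes, then whatever governs a parent's capacity to be involved before any intervention acts is a plausible determinant of the primary outcome. Maternal age, parity (older children at home), social position and distance from the unit are examples. Units serve different populations, and those populations can change over fifteen birth years. Adjusting for how sick or how premature the infants are does not balance the families.

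An unadjusted difference in parent mix would be attributed to the training program or the architecture. The plan says its results should inform future investment in neonatal care, so a wrong sign or size would carry into resource decisions.

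**Working it through.** The plan states no effect size, standard deviation or sample size for this comparison, so there is no figure to reproduce. The check is whether the planned model already removes the bias.

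**Bias formula.** Let β be the effect on length of stay of an omitted pre-birth parental factor, given the listed covariates, and let p be its prevalence.
- Ever/never comparison of units: bias ≈ β × (p in intervention units − p in control units).
- Before/after comparison within units, relative to controls: bias ≈ β × [(change in p in intervention units) − (change in p in control units)].

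The first is non-zero whenever parent mix differs between unit groups. The second is zero if each unit's mix is constant in time, and non-zero if mix shifts along with adoption. The sign follows β and the gap, so either direction is possible.

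**What the documents supply.** They give neither β nor p for any parental characteristic. The two formulas can show which designs are exposed, but not by how many days.

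**Illustrative simulation.** The true intervention effect was set to 0. None of the following inputs comes from the documents except the unit counts, the years and the number 15, which is borrowed only as a scale:
- 15 intervention units (11 + 4, assuming no overlap) and 10 control units, births 2006–2020, 30 infants per unit-year
- adoption years 2012–2018
- residual SD 15 days, unit SD 2 days
- a binary factor with β = −15 days and a 10-point prevalence gap
- calendar year in every model, 60 replicates

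The full product is −15 × 0.10 = −1.50 days. Because that scale is arbitrary, the useful output is the share of it that survives as a spurious effect (mean estimate ÷ −1.50).

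| Model | Mix constant in time | Mix shifts with intervention |
|---|---|---|
| Ever/never exposure, random unit intercept | −1.50 (100%) | −0.72 (48%) |
| Before/after exposure, random unit intercept | −0.28 (19%) | −1.51 (101%) |
| Before/after exposure, fixed unit effects | −0.06 (4%) | −1.50 (100%) |
| Before/after exposure, random intercept, factor in model | −0.07 (5%) | +0.04 (−3%) |

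Monte Carlo standard errors are 0.05 to 0.11 days, so the third-row value of −0.06 and both fourth-row values are compatible with zero at this precision. The 19% depends on the assumed SDs and unit sizes.

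**Reading.** The unit term removes the bias only in one cell of the first three rows: before/after exposure, fixed unit effects, stable parent mix. Adjusting for the factor removes it in both columns. The simulated factor is measured without error; register variables would do this only in part.

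**The case against.** The strongest objection is that unit is already in the model. The four single-family-room units converted from 2014 to 2019, inside the 2006–2020 cohort, so births before conversion exist and a within-unit contrast is possible. This stands in part. With that contrast, stable differences in parent mix drop out. But the plan does not commit to it, the Outcomes wording is closer to an ever/never comparison, and no unit term deals with mix that shifts over time. It also stands that unstated exposure timing is the more basic gap, and that adding covariates does not close it.

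Second, the list is of variables to be considered, and unspecified background data are requested. Parental items are therefore unnamed, not excluded. That is fair, but a model built from the list as written would contain none.

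Third, the Background argues that Finnish leave and health care equalise opportunity. A reader might infer that the plan uses this to justify leaving parents out of the model. The text does not say so: the sentence explains why conditions are better controlled than in previous studies. Equally, it concerns access and does not show that parity, age or distance is balanced across units.

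Fourth, a reader might multiply the cited 15 days by an assumed 10-point gap, obtain 1.5 days, and set it against the cited 3.9-day effect (1.5/3.9 = 38%). The documents do not support that. The 15 days contrasts participating with non-active mothers. Participation is a mediator here, and its effect is not the effect of parity, age, social position or distance. The gap is not in the documents either, and against the 10 days cited for single-family rooms the same product is 15%.

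**Conclusion.** The omission is real and worth correcting before analysis. The primary comparison is non-randomised, the interventions are meant to act through parents, and no pre-birth parental characteristic is listed. The protection offered by the unit term depends on a specification that the plan does not state, and it does not extend to changes in parent mix over time.

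The size is unknown. Bias requires that parent mix differ by intervention status, or change with it, and that it affect length of stay beyond the listed covariates. The documents give no data on either condition. A reader might infer that parent mix will appear as an intervention effect, or that the bias favours the hypothesis. Neither follows: the documents support only that it could bias the result, and the opposite imbalance would hide a true effect.

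**What to change.** In the Statistical analysis section, add as set adjustment terms the parental characteristics fixed before birth that the linked registers hold: for example maternal age and parity, and socioeconomic group and residence relative to the unit if those fields exist there. Tabulate them by unit group and by period. Report length of stay with and without them. State that measured parental presence will not be adjusted for, because it is the route through which the interventions are meant to work.

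The cost is a few more register fields and model terms, some missing values, and possibly an update to the data permit, which the Timeline says was applied for in 2020. The documents do not list the register fields, so availability is an assumption. If the two sets of results agree, the plan's view that parents are comparable gains support.

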## **Methods**

The study population will consist of all newborn infants born from January 1st 2006 to December 31st 2020, who have needed care in a neonatal unit immediately after birth. These infants will be identified from the Hospital Discharge Register. Data on vital background data, birth details, diagnoses, length of stay, growth parameters and outpatient visits will be obtained from the Hospital Discharge Register and the Medical Birth Register. These data will be linked through the infants' personal identification codes, which will be replaced by a pseudonymized ID-number before delivering the data to the research group. Planned subgroup analyses will be done for preterm infants and for infants with significant congenital anomalies.

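### Discharge length and head circumference have no like-for-like birth covariate: birth weight z-score is the only size-at-birth candidate in the model

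*Combined protocol and SAP*

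**What the plan says.** The Outcomes section of the combined protocol and SAP lists two sets of secondary growth outcomes: "Growth parameters (weight, length, head circumference) at discharge compared to national standards" and "Change in growth parameters from birth to discharge". The comparison, stated there for the primary outcome and with no other given, is between units and not randomised: "Comparisons will be made between infants cared for in intervention units and those cared for in non-intervention units".

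The Statistical analysis section describes a "linear mixed model-approach to account for the effect of unit, degree of prematurity and intervention". It then gives a single list of six candidates, namely "gestational age at birth, mode of delivery, birth weight z-score, plurality, neonatal morbidities, and receipt of antenatal steroids". Neither birth length nor birth head circumference is on it. The list is tentative, as its lead-in shows: "Variables that will be considered for inclusion into the model are". No section gives a separate model or covariate list for the growth outcomes.

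On data, the Methods section says that "growth parameters and outpatient visits will be obtained from the Hospital Discharge Register and the Medical Birth Register".

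**The concern.** Three body measures are outcomes at discharge, but the candidate list holds the birth value of only one. Birth weight z-score is a like-for-like baseline for weight. For length and head circumference it is a proxy, and an imperfect one, for example where growth restriction has spared the head.

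This matters because unit groups are not balanced by design. If infants in intervention units differ from the others in birth length or head size at a given birth weight, part of that difference carries through to discharge and is read as an intervention effect. Early growth is one of the research questions, with a directional hypothesis. The change outcome does use the birth values, but subtraction is not the same as adjustment. When birth and discharge values correlate below 1, subtraction takes away more of the birth difference than persists. The two planned growth outcomes could then disagree purely because of how they handle baseline.

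**Working it through.** **Baseline use by outcome, if the plan is followed as written**

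| Measure | Discharge outcome | Change outcome |
|---|---|---|
| Weight | own birth value is a candidate covariate | birth value subtracted and a candidate covariate |
| Length | birth weight z-score only | birth value subtracted, not a candidate covariate |
| Head circumference | birth weight z-score only | birth value subtracted, not a candidate covariate |

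The change column shows that birth length and birth head circumference have to be obtained in any case.

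**Inputs for size.** The documents give no SD, correlation or effect size for growth, so there is no figure of the plan's to reproduce. The following are assumptions, for head circumference only, with all variables as z-scores of SD 1:

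- r1, discharge head with birth head: 0.5 to 0.7, central 0.60
- r2, discharge head with birth weight: 0.40 to 0.50, central 0.45
- r12, birth head with birth weight: 0.70 to 0.75, with 0.75 used in the central case

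**Residual variance.** With birth weight z-score alone, R² = r2². With both covariates, R² = (r1² + r2² − 2·r1·r2·r12)/(1 − r12²). The residual variance ratio is (1 − R² with both)/(1 − r2²).

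- Central (0.60, 0.45, 0.75): R² = (0.36 + 0.2025 − 0.405)/0.4375 = 0.36, against 0.2025. Ratio 0.64/0.7975 = 0.80, a 20% reduction.
- Smallest (0.5, 0.5, 0.75): R² = 0.125/0.4375 = 0.286, against 0.25. Ratio 0.714/0.75 = 0.952, a 4.8% reduction.
- Largest (0.7, 0.4, 0.75): R² = 0.23/0.4375 = 0.526, against 0.16. Ratio 0.474/0.84 = 0.565, a 43.5% reduction.

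A grid over all combinations of the three ranges confirms that the last two are the extremes.

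**Bias from a birth difference that birth weight does not carry.** Suppose the groups differ by 0.1 SD in birth head circumference and are balanced on birth weight z-score. The coefficient of birth head given birth weight is b = (r1 − r2·r12)/(1 − r12²). The discharge model with birth weight only is off by 0.1·b. The change score adjusted for birth weight only is off by 0.1·(b − 1).

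- Central: b = (0.60 − 0.3375)/0.4375 = 0.60. Discharge +0.06 SD; change −0.04 SD.
- Over the ranges, b runs from 0.125/0.4375 = 0.29 to 0.40/0.4375 = 0.91. Discharge +0.03 to +0.09 SD; change −0.07 to −0.01 SD.

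The signs are opposite throughout. With the birth head z-score in the model, both biases are zero in this calculation, which takes birth head circumference as measured without error and considers no other confounding. The 0.1 SD is itself illustrative; the documents show no such imbalance.

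**When the two estimates coincide.** If the birth z-score is a covariate, subtracting it from the outcome lowers its own coefficient by 1 and leaves every other coefficient unchanged. This needs the same z-score scale, the same covariates and the same infants in both models. The Outcomes section does not say whether change is measured in z-scores.

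**The case against.** The strongest reply is that the list names variables to be considered for one unspecified model serving every outcome, and may have been written with length of stay in mind. A reader might infer that the plan has decided against adjusting for birth length and head circumference. The documents do not support that: this is a missing outcome-specific specification, not a refusal. The gap remains, because neither variable is among the candidates, and if the list was meant only for length of stay, growth has no stated covariates at all.

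A reader might also infer that the birth values go unused. They do not: they enter the change outcome by subtraction. What is missing is their use as covariates, which matters most for the discharge outcomes.

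Third, it is tempting to say that own-baseline adjustment removes the bias and should replace the change analysis. That goes too far. In non-randomised groups, change-score and baseline-adjusted analyses answer different questions, and neither is unbiased without assumptions (Lord's paradox). Error in routinely recorded birth length or head circumference leaves part of the imbalance in place. This limits the claim to a reduction in bias and argues for keeping the change outcome.

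Finally, the gain could be trivial: at the low end of the assumed correlations it is about 5% of residual variance, and clustering shrinks what reaches the unit-level effect. That stands, and it is why this is a refinement and not a serious defect.

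**Conclusion.** The point holds as a minor improvement. As written, the comparisons of discharge length and discharge head circumference between non-randomised unit groups have no like-for-like baseline adjustment, although the values needed for it are required elsewhere in the plan. The central case is a 20% cut in residual variance, and 0.06 SD of bias avoided per 0.1 SD of birth imbalance that birth weight does not carry. Both figures rest wholly on assumed correlations for head circumference; none was worked out for length. The bias figure also assumes no measurement error. The primary outcome, length of stay, and the discharge weight comparison are unaffected.

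**What to change.** In the Statistical analysis section, state that the model for discharge length includes birth length z-score, and the model for discharge head circumference includes birth head circumference z-score, each alongside birth weight z-score. Discharge weight needs no addition, since birth weight z-score already serves. Keep the change outcome as planned and, if wanted, report an own-baseline-adjusted version beside it. State the scale on which change is measured.

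The cost is one or two sentences and no new variables. The drawback is missing data: infants without a recorded birth length or head circumference can contribute to the discharge analysis now, but would leave the adjusted one. Name the handling in advance, for example multiple imputation, or also report the model without that covariate.
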